5.4 Secondary Endpoints

Secondary objectives include assessments of PK, IM, pharmacodynamics, and antitumor activity of MEDI-573.

5.4.1 Pharmacokinetics of MEDI-573

The PK of MEDI-573 will be assessed by noncompartmental approach using a validated computer software package [REDACTED]. The noncompartmental pharmacokinetic parameters to be obtained and reported include, but are not limited to: C_{max} , T_{max} , and AUC, if the data allow. Descriptive statistics will be provided by cohort.

5.4.2 Immunogenicity of MEDI-573

Immunogenicity of MEDI-573 will be assessed and summarized descriptively by cohort.

5.4.3 Pharmacodynamics of MEDI-573

Suppression profiles of both IGF-1 and IGF-2 post administration of MEDI-573 in relation to time course of antibody concentrations in serum will be evaluated. Pharmacodynamic assessment of MEDI-573 treatment on the levels of circulating soluble protein biomarkers may include but are not limited to IGF receptor type 1 (IGF-1R), insulin receptor substrate-1 (IRS-1), mitogen-activated protein kinase (MAPK), insulin receptor (IR), antigen identified by monoclonal antibody Ki-67 (Ki67), caspase 3, and/or protein kinase B signaling protein (pAkt). TUNEL analyses may also be performed. Tissues to be assayed will include archived tumor biopsies (optional), and biopsies obtained during surgical procedures conducted in the course of routine patient care (optional). In the dose-expansion phase, additional samples will be obtained from subjects who may be undergoing cystoscopic procedures (optional); exfoliated cells collected in voided urine, catheterized urine, and/or bladder washings; and biopsies of bladder cancers or of bladder cancer metastatic deposits (with image guidance as needed). The biopsies of bladder cancers or bladder cancer metastatic deposits will be required before and after treatment with study drug for all subjects in the dose-expansion phase of the study. Samples will be collected at two timepoints; prior to the first treatment of Cycle 1, and after the last dose on Cycle 1 but prior to administration of the first dose of Cycle 2. Evaluation of the relationship of IGF pathway-related factors including IR-A expression levels using whole genome array and subject response to study treatments will be

performed on available fresh and/or archival tumor samples from subjects in the dose-escalation phase of the study and on fresh and archival tumor samples obtained in the dose-expansion phase of the study

In the dose expansion phase of the study, expression of IGF pathway factors including gene expression of IGF-1R, IR-A, IR-B and IGF response and modulation of the IGF-1R pathway in tumor cells. Expansion phase analyses include evaluating the relationship of IGF pathway-related components at the mRNA and miRNA level, as well as IR-A mRNA level in tumor biopsies obtained pre- and post-MEDI-573 treatment [REDACTED] s [REDACTED]. Additionally, protein expression levels will be evaluated using immunohistochemistry in tumor biopsies obtained pre- and post-MEDI-573 treatment. These studies serve the purpose of evaluating target expression and modulation in response to treatment with MEDI-573 and the downstream effect of neutralizing IGF in tumor tissue. Correlation between target expression and modulation in tumor tissue and clinical activity will also be evaluated. If applicable, a CAST assay will be performed to evaluate potential point mutations in the key genes downstream of IGF signaling pathway to evaluate their correlations with clinical activity of MEDI-573.

5.4.4 Antitumor Activity of MEDI-573

The antitumor activity of MEDI-573 will be assessed based on ORR, time to response TTR, DR, TTP, PFS, and OS.

Objective response rate is defined as the proportion of subjects with confirmed CR or confirmed PR according to RECIST guidelines. Confirmed responses are those that persist on repeat imaging study ≥ 4 weeks after the initial documentation of response.

Time to response will be measured from the start of treatment with MEDI-573 to the first documentation of objective response and will only be assessed in subjects who have achieved objective response.

Duration of response will be defined as the duration from the first documentation of objective response to the first documented disease progression. Duration of response will be censored on the date of last tumor assessment documenting absence of disease progression for subjects who have no documented progression prior to data cutoff, dropout, or the initiation of alternate anticancer treatment. Duration of response will only be calculated for the subgroup of subjects with an objective response.

Time to progression (TTP) will be measured from the start of treatment with MEDI-573 until the documentation of disease progression. Disease progression is defined according to RECIST guidelines. Time to progression will be censored on the date of last tumor assessment documenting absence of tumor progression for subjects who have no documented progression prior to data cutoff, dropout, or the initiation of alternate anticancer treatment. Subjects having no tumor assessments after the start of treatment with MEDI-573 will have TTP censored on the first date of treatment with MEDI-573.

Progression-free survival will be measured from the start of treatment with MEDI-573 until the documentation of disease progression or death due to any cause, whichever occurs first. Disease progression is defined according to RECIST guidelines. Progression-free survival will be censored on the date of last tumor assessment documenting absence of tumor progression for subjects who have no documented progression and are still alive prior to data cutoff, dropout, or the initiation of alternate anticancer treatment. Subjects having no tumor assessments after the start of treatment with MEDI-573 will have PFS censored on the first date of treatment with MEDI-573.

Overall survival (OS) will be determined as the time from the start of treatment with MEDI-573 until death. For subjects who are alive at the end of study or lost to follow-up, OS will be censored on the last date when subjects are known to be alive.

The time to event data including TTR, DR, TTP, PFS, and OS will be evaluated using Kaplan-Meier methods.

6 Data Collection and Monitoring

The study will be monitored by the Sponsor or its designee on a regular basis throughout the study period. During monitoring visits, the investigator will provide direct access to all source documentation relevant to the subject's participation in the study. Source documentation includes, but is not limited to, the subject's clinic and/or office chart, hospital chart, informed consent forms, treatment notes, laboratory reports, pharmacy records, radiographs, and any other records maintained to conduct and evaluate the clinical study. The investigator must also ensure that direct access to study documents be made available for study-related audits, IRB/IEC review, or regulatory inspection.

Data recorded on source documents will be transcribed onto a validated data collection instrument (a paper case report form or electronic data screen) provided by the Sponsor or

designee. The investigator must ensure the accuracy and completeness of the data reported, and its consistency with the source documentation.

The primary source document for this study will be the subject's medical record. If separate research records are maintained by the investigator(s), both the medical record and the research records will be monitored/audited for the purposes of the study.

Study documents (including subject records, copies of collected data, study notebook, and pharmacy records) must be kept secured in accordance with Sponsor policies and applicable regulatory requirements for a period of 2 years following marketing of MEDI-573 or for 2 years after centers have been notified that the IND has been discontinued. There may be other circumstances for which the Sponsor is required to maintain study records and, therefore, the Sponsor should be contacted prior to removing study records for any reason.

7 Human Subjects

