The following evaluations will be performed every 2 cycles (ie, every 6 weeks), unless otherwise indicated, starting at Cycle 3 (eg, Cycle 3, Cycle 5, etc.):

- 1) Complete physical examination
- 2) AE/SAE assessment
- 3) Concomitant medications
- 4) Evaluation of disease
 - CT or MRI scans

End of Treatment (All Subjects Unless Otherwise Specified)

The following evaluations will be performed at the time the subject completes therapy or is withdrawn / discontinued from the study therapy, or at the time of the first objective disease progression, whichever comes first. These procedures do not need to be repeated if completed within 14 days of discontinuation of participation.

- 1) Complete physical examination
- 2) Weight
- 3) Vital signs
- 4) Blood and tissue collection
 - Hematology (CBC with differentials, platelets, and HgA1c)
 - Serum chemistry (AST/ALT, total bilirubin, creatinine, alkaline phosphatase, sodium, potassium, chloride, phosphorus, calcium, glucose, albumin, magnesium, LDH, TSH)
 - Serum concentration of MEDI-573
 - Blood biomarker analysis
 - Whole blood RNA analysis
 - Circulating tumor cells
 - Urinalysis (routine urinalysis with microscopy)
 - Exfoliated urothelial cells and analysis of soluble factors (from urine or bladder washes; dose-expansion cohort only)
- 5) AE/SAE assessment
- 6) Concomitant medications

- 7) ECG (12-lead). All ECGs performed will be obtained in triplicate, ie, 3 ECGs should be obtained within approximately a 5-minute time interval.
- 8) Disease evaluations (these procedures do not need to be repeated if they have been performed within 14 days of disease progression or treatment discontinuation)
 - CT or MRI scans
 - Physical examination
 - Karnofsky performance status

21 Days Post-therapy (+ 3 days; All Subjects)

- 1) Serum concentration of MEDI-573
- 2) Blood biomarker analysis

30 Days Post-therapy (+ 3 days; All Subjects)

The following evaluations will be performed at 30 days (+ 3 days) after the last dose of MEDI-573:

- 1) Complete physical examination
- 2) Weight
- 3) Vital signs
- 4) ECG (12-lead) All ECGs performed will be obtained in triplicate, ie, 3 ECGs should be obtained within approximately a 5-minute time interval.
- 5) Blood collection
 - Hematology (CBC with differentials, platelets)
 - Serum chemistry (AST/ALT, total bilirubin, creatinine, alkaline phosphatase, sodium, potassium, chloride, phosphorus, calcium, glucose, albumin, magnesium, LDH, and TSH)
 - Serum concentration of MEDI-573

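### Duration of response leaves out death, so a responder who dies without documented progression is censored as if still in response

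*Protocol*

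**What the plan says.** Section 5.4.4 defines the event for duration of response (DR) in one sentence: "Duration of response will be defined as the duration from the first documentation of objective response to the first documented disease progression". The censoring rule follows: "Duration of response will be censored on the date of last tumor assessment documenting absence of disease progression". It applies to "subjects who have no documented progression prior to data cutoff, dropout, or the initiation of alternate anticancer treatment". Death appears neither as an event nor as a separate reason for censoring. The Study Abstract, under Secondary Endpoints, gives the same definition.

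For PFS, the same section measures time "until the documentation of disease progression or death due to any cause, whichever occurs first". It censors only subjects who "have no documented progression and are still alive prior to data cutoff, dropout, or the initiation of alternate anticancer treatment".

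On estimation, the section says: "The time to event data including TTR, DR, TTP, PFS, and OS will be evaluated using Kaplan-Meier methods". No competing-risk method is named for DR. The statistical analysis plan is not at hand, but the protocol itself fixes the event and the censoring rule.

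**The concern.** A responder who dies before progression is documented meets the condition of having no documented progression, and so is censored at the last progression-free assessment. Kaplan-Meier then lets the responders who remain stand in for that subject, as though the response were continuing. In advanced cancer, death before documented progression is unlikely to be independent of the course of the disease, so this censoring is hard to defend as uninformative.

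Such deaths are possible here. Section 3.1.1 asks only for a life expectancy of at least 12 weeks and a Karnofsky score of at least 60. After treatment stops for reasons other than progression or new anticancer therapy, Section 3.6 schedules scans only every 3 months.

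DR is calculated in responders only, within a study of 21 to 42 evaluable escalation subjects and about 20 expansion subjects. One death can therefore change the curve visibly. What is at stake is how a reader interprets the durability of any responses seen.

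**Working it through.** The protocol gives no expected DR, response rate or death rate, so there is no figure of its own to reproduce. Every numerical input in steps 3 to 5 is an assumption, except the 6-week scan interval.

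**1. The rules side by side (Section 5.4.4).**

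| Measure | Event | Must a censored subject be alive? |
|---|---|---|
| DR | progression | no |
| TTP | progression | no |
| PFS | progression or death | yes |

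TTP and PFS form a pair, one without death and one with it. DR has no counterpart that counts death.

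**2. Direction.** Let n responders be at risk just after the last scan of the one who later dies. Let d of the others have documented progression between that scan and the death, with no other censoring in the interval. Over that interval the curve is multiplied as follows:

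- Protocol rule: (n - 1 - d)/(n - 1).
- Death as an event: (n - d)/n up to the death, times (n - d - 1)/(n - d) at the death, which is (n - 1 - d)/n.

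The ratio is n/(n - 1), which exceeds 1. Risk sets are the same afterwards, so the protocol curve stays higher by this factor from the death onward, as long as another responder remains at risk. Between the last scan and the death, the protocol curve can be briefly lower if d > 0 (1 - d/(n - 1) against 1 - d/n), because censoring is dated back to the scan.

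**3. Small example.** Four responders: progression at weeks 12, 18 and 30, and one death at week 15 with the last scan at week 12.

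- Protocol rule: week 12, 1 - 1/4 = 0.75; week 18, 0.75 × (1 - 1/2) = 0.375; week 30, 0. Median: week 18.
- Death as an event: week 12, 0.75; week 15, 0.75 × (1 - 1/3) = 0.50; week 18, 0.50 × (1 - 1/2) = 0.25; week 30, 0. Median: week 15.

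Here n = 3 and d = 0, so step 2 predicts a ratio of 3/2 = 1.5. At week 18, 0.375/0.25 = 1.5.

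**4. Constant hazards.** Take hazards p for progression and m for death without it, acting independently, with s = m/(p + m). The median is ln 2/p with deaths censored and ln 2/(p + m) with deaths counted. The ratio is (p + m)/p = 1/(1 - s).

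- s = 10%: 1/0.9 = 1.11; a 6-month median becomes 6.7 months.
- s = 20%: 1/0.8 = 1.25; 7.5 months.
- s = 30%: 1/0.7 = 1.43; 8.6 months.

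**5. With the scan schedule.** Section 3.6 sets the on-treatment interval: "The following evaluations will be performed every 2 cycles (ie, every 6 weeks), unless otherwise indicated". A simulation of 200,000 responders per setting used a median of 26 weeks to progression or death, recorded progression at the next 6-week scan, and censored deaths at the preceding scan. Each pair shows the protocol rule against death as an event.

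| Deaths among first events | Median, weeks | Ratio | Curve at 52 weeks |
|---|---|---|---|
| 10.8% | 30 v 30 | 1.00 | 0.315 v 0.274 |
| 21.2% | 36 v 30 | 1.20 | 0.360 v 0.273 |
| 31.7% | 42 v 30 | 1.40 | 0.409 v 0.271 |

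At the lowest share the scan grid hides the shift in the median, but the curve still moves.

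**The case against.** The strongest reply is that a progression-only DR is coherent. TTP is defined in the same way, nobody objects to that, and the protocol nowhere says that DR should measure time alive and progression-free. On this view, DR and PFS differ for the same reason that TTP and PFS differ. Deaths are counted in OS, and deaths before progression in PFS. DR is one of six antitumor measures under a secondary objective, and no stated decision on escalation, Cohort 7 or expansion uses it. With few responders, individual outcomes can be read directly.

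Much of this stands. The DR and PFS rules are different choices and do not contradict each other. The ratio 1/(1 - s) compares two different quantities. It assumes that death and progression are independent, so it does not measure bias from informative censoring.

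What does not stand is the parallel with TTP. PFS is reported beside TTP and counts death, whereas DR has no such companion. Even as a progression-only measure, DR by Kaplan-Meier needs deaths to be uninformative about later progression, and the protocol offers no reason to expect that.

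**Conclusion.** The point holds in conditional form, as a low-cost improvement. The wording censors a responder who dies without documented progression. If that happens, the DR curve from that death onward lies above the curve for time alive and progression-free in responders, as long as another responder remains at risk. If it does not happen, the two curves are identical.

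A reader might infer that DR in this trial will be overstated, or overstated by 11% to 43%. The documents support neither. They give no number of responders and no death rate, and the percentages rest on assumed death shares and constant hazards. At a death share of about 10%, the simulated median with 6-week scans did not move at all. The word overstated also applies only relative to progression or death as the target, which is the standard the protocol uses for PFS but does not state for DR. The primary safety and MTD/OBED objectives are untouched.

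**What to change.** In Section 5.4.4 and in the Study Abstract, let DR run from the first documentation of response and take over the PFS end point: "until the documentation of disease progression or death due to any cause, whichever occurs first". Align the DR censoring rule with PFS, so that it covers only responders who "have no documented progression and are still alive prior to data cutoff, dropout, or the initiation of alternate anticancer treatment", still censored at the last progression-free assessment. Leave TTP unchanged as the measure that excludes death.

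The cost is two short edits in each place. No new data are needed, since survival status is already collected in follow-up under Section 3.6. Reported DR may be shorter than under the present rule if a responder dies without documented progression.

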7.1 Ethics and Regulatory Considerations

This study will be conducted accordance with the International Conference on Harmonisation (ICH) guidelines on Good Clinical Practice (GCP), the GCP's applicable to any region where the study is conducted and in accordance with the ethical principles set forth in the Declaration of Helsinki. GCP is defined as a standard for the design, conduct, performance, monitoring, auditing, recording, analysis, and reporting of clinical studies in a way that provides assurance that the data and reported results are credible and accurate and that the rights, safety, and well-being of study subjects are protected.

The protocol will be reviewed and approved by the Institutional Review Board (IRB) or Independent Ethics Committee (IEC) of each participating center prior to study initiation. Serious adverse events regardless of causality will be reported to the Sponsor and to the IRB/IEC, and the investigator will keep the IRB/IEC informed as to the progress of the study.

The investigator will explain the nature of the study and will inform the subject/legal representative that participation is voluntary and that they can withdraw/can withdraw their child at any time. Written informed consent will be obtained from each subject/legal representative prior to the screening procedures required for entry into the study. A copy of the signed consent form will be given to every subject/legal representative and the original will be maintained with the subject's records.

To maintain confidentiality, all laboratory specimens, evaluation forms, reports and other records will be identified by a coded number and initials only. All study records will be kept in a locked file cabinet and code sheets linking a subject's name to a subject identification number (SID) will be stored separately in another locked file cabinet. Study records may be maintained electronically and require the same security and confidentiality as paper. Clinical information will not be released without written permission of the subject/legal representative, except as necessary for monitoring by regulatory authorities or the Sponsor of the clinical study. The principal investigator must also comply with all applicable privacy regulations (eg, Health Insurance Portability and Accountability Act of 1996, EU Data Protection Directive 95/46/EC).

7.2 Institutional Review Board (IRB) or Independent Ethics Committee (IEC)

A list of IRB/IEC members should be obtained by the investigator and provided to the Sponsor.

Any documents that the IRB/IEC may need to fulfill its responsibilities, such as protocol amendments, and information concerning subject recruitment, payment or compensation procedures, or information from the Sponsor will be submitted to the IRB/IEC. The IRB/IEC's written unconditional approval of the study protocol, the informed consent form, and any other written materials to be provided to subjects will be in the possession of the investigator and the Sponsor before the study is initiated. The IRB/IEC's unconditional approval statement will be transmitted by the investigator to the Sponsor prior to shipment of investigational product supplies to the site. This approval must refer to the study by exact protocol title and number, and should identify the documents reviewed and the date of review.

Protocol modifications or changes may not be initiated without prior written IRB/IEC approval except when necessary to eliminate immediate hazards to the subjects or when the change(s) involves only logistical or administrative aspects of the study. Such modifications will be submitted to the IRB/IEC and written verification that the modification was submitted should be obtained.

The IRB/IEC must be informed by the principal investigator of informed consent form changes or revisions of other documents originally submitted for review; serious and/or unexpected adverse experiences occurring during the study; new information that may affect

adversely the safety of the subjects or the conduct of the study; an annual update and/or request for re-approval; and when the study has been completed.

7.3 Informed Consent

Freely given informed consent will be obtained and documented for all subjects under this protocol (or a subject's legally authorized representative, if the subject is unable to provide informed consent) in accordance with the ICH guidelines on Good Clinical Practice (GCP), the GCP's applicable to any region where the study is conducted and in accordance with the ethical principles set forth in the Declaration of Helsinki.

Information should be given in both oral and written form, and subjects or their legal representatives must be given ample opportunity to inquire about details of the study. The written informed consent document will comply with the ICH guidelines on GCP, the GCP's applicable to any region where the study is conducted and in accordance with the ethical principles set forth in the Declaration of Helsinki.

Subjects or their legal representatives must be informed that the study involves research. They must be informed about the aims, expected benefits, possible risks (including a statement that the particular treatment or procedure may involve risks to the subject or the fetus of the subject, if the subject should become pregnant) that are currently unforeseeable. They must also be informed of the study procedures to be followed and alternative treatment available to them. Subjects or their legal representatives must receive an explanation as to whether any compensation and any medical treatments are available if injury occurs and, if so, what they consist of, or where further information may be obtained. They must be informed whom to contact for answers to any questions relating to the research project. The subjects or their legal representatives must be informed that participation is voluntary and that they are free to withdraw or withdraw their child from the study for any reason at any time, without penalty or loss of benefits to which they are otherwise entitled. The extent of the confidentiality of subject records must be defined, and subjects or their legal representatives must be informed that applicable data protection legislation will be complied with. They must be informed that the monitor(s), auditor(s), IRB/IEC members, and the regulatory authorities will be granted direct access to the subject's original medical records for verification of clinical study procedures and/or data, without violating the confidentiality of the subject, to the extent permitted by the applicable laws and regulations and that, by signing a written informed consent form, the subject or the subject's legally acceptable representative is authorizing such access.

The consent form generated by the investigator must be approved by the IRB/IEC and be acceptable to the Sponsor.

Consent forms must be written so as to be understood by the prospective subject/legal representative. Informed consent will be documented by the use of a written consent form approved by the IRB/IEC and signed and dated by the subject or the subject's legally authorized representative, and by the person who conducted the informed consent discussion. The signature confirms the consent is based on information that has been understood. Each subject's signed informed consent form must be kept on file by the investigator for possible inspection by Regulatory Authorities and/or the Sponsor's professional and Regulatory Compliance persons. The subject or the subject's legally acceptable representative should receive a copy of the signed and dated written informed consent form and any other written information provided to the subject, and should receive copies of any signed and dated consent form updates and any amendments to the written information provided to subjects.

8 Study Completion

All materials or supplies provided by the Sponsor will be returned to the Sponsor upon study completion. The investigator will notify the IRB/IEC when the study has been completed.

9 Publications

Publication by the site of any data from this study must be carried out in accordance with the clinical study agreement.

10 Changes in the Protocol

The protocol may not be modified without written approval of the Sponsor. All changes to the protocol must be submitted to the applicable regulatory agencies and IRBs/IECs, and must be approved by the IRB/IEC prior to their implementation. Documentation of IRB/IEC approval must be sent to the Sponsor immediately upon receipt.

11 References

